#### **DEPRESSED MOOD**

(sadness, hopeless, helpless, worthless)

- 0- Absent
- 1- These feeling states indicated only on questioning
- 2- These feeling states spontaneously reported verbally
- 3- Communicates feeling states non-verbally—i.e., through facial expression, posture, voice, and tendency to weep

4- Patient reports VIRTUALLY ONLY these feeling states in his spontaneous verbal and nonverbal communication

#### **FEELINGS OF GUILT**

- 0- Absent
- 1- Self-reproach, feels he has let people down
- 2- Ideas of guilt or rumination over past errors or sinful deeds
- 3- Present illness is a punishment. Delusions of guilt
- 4- Hears accusatory or denunciatory voices and/or experiences threatening visual hallucinations

# SUICIDE

2

- 1 Feels life is not worth living
- 2 Wishes he were dead or any thoughts of possible death to self
- 3 Suicidal ideas or gesture
- 4 Attempts at suicide (any serious attempt rates 4)

#### 4

5

6

7

#### **INSOMNIA EARLY**

- 0- No difficulty falling asleep
- 1- Complains of occasional difficulty falling asleep-i.e., more than 1/2 hour

2- Complains of nightly difficulty falling asleep

#### **INSOMNIA MIDDLE**

0- No difficulty

1- Patient complains of being restless and disturbed during the night

2- Waking during the night—any getting out of bed rates 2 (except for purposes of voiding)

#### **INSOMNIA LATE**

0- No difficulty

1- Waking in early hours of the morning but goes back to sleep

2- Unable to fall asleep again if he gets out of bed

#### WORK AND ACTIVITIES

0- No difficulty

- 1- Thoughts and feelings of incapacity, fatigue or weakness related to activities; work or hobbies
- 2- Loss of interest in activity; hobbies or work—either directly reported by patient, or indirect in listlessness, indecision and vacillation (feels he has to push self to work or activities)
- 3- Decrease in actual time spent in activities or decrease in productivity. In hospital settings the mark "3" is stated if patient's activity is exhibited during at least 3 hours per day (working in a hospital or a hobby)

4- Stopped working because of present illness.

In hospital settings the mark "4" is stated if patient does not exhibit activity or does not cope even with routine household activity without assistance.

#### **RETARDATION: PSYCHOMOTOR**

(slowness of thought and speech; impaired ability to concentrate; decreased motor activity)

- 0- Normal speech and thought
- 1- Slight retardation at interview
- 2- Obvious retardation at interview
- 3- Interview difficult
- 4- Complete stupor

#### AGITATION

- 0-None
- 1- Fidgetiness
- 2- Playing with hands, hair, etc.
- 3- Moving about, can't sit still
- 4- Hand wringing, nail biting, hair-pulling, biting of lips

10

8

9

#### **ANXIETY (PSYCHOLOGICAL)**

- 0- No difficulty
- 1- Subjective tension and irritability
- 2- Worrying about minor matters
- 3- Apprehensive attitude apparent in face or speech
- 4- Fears expressed without questioning

#### **ANXIETY SOMATIC**

(Physiological concomitants of anxiety: **gastrointestinal** - dry mouth, "butterflies," indigestion, stomach cramps, belching, diarrhea;

cardiovascular – palpitations, headache; respiratory – hyperventilation, dyspnea; urinary frequency; sweating)

- 0- Absent
- 1- Mild
- 2- Moderate
- 3- Severe
- 4- Incapacitating

12

13

#### SOMATIC SYMPTOMS (GASTROINTESTINAL)

- 0-None
- 1- Loss of appetite but eating without encouragement from others. Food intake about normal
- 2- Difficulty eating without urging from others. Requirement in laxatives and drugs for relief of gastrointestinal symptoms

#### SOMATIC SYMPTOMS GENERAL

- 0-None
- 1- Heaviness in limbs, back or head. Backaches, headache, muscle aches. Loss of energy and fatigability
- 2- Any clear-cut symptom rates

#### **GENITAL SYMPTOMS**

- 0- Absent
- 1- Mild loss of libido
- 2- Severe menstrual disturbances

14

- 0- Not present
- 1- Self-absorption (bodily)
- 2- Preoccupation with health
- 3- Frequent complaints, requests for help, etc.
- 4- Hypochondriacal delusions

#### LOSS OF WEIGHT (either A or B is used)

16A

#### A. When rating by history:

- 0- No weight loss
- 1- Probably weight loss associated with present illness
- 16B2- Definite (according to patient) weight loss
  - 3- Not assessed

#### B. If loss of weight is observed each week and is actual now

- 0- Less than 0.5 kg per week
- 1- More than 0.5 kg per week
- 2- more than 1 kg per week
- 3- Not assessed

#### 17

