## Study variables

## **Primary variables:**

• Mean change from baseline (BL) in total HAMD-17 score assessed at week 8 of the observational period.

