#### Secondary variables:

- % of patients defined as responders to the treatment (HAMD-17 total score decrease ≥ 50%) at week 8 of the observational period.
- % of patients achieving disease remission (defined as HAMD-17 total score < 7) at week 8 of the observational period.
- Mean change from BL in HAMD-17 point 10 "psychological anxiety" assessed at week 8 of the observational period.
- Mean change from BL in HAMD-17 point 11 "somatic anxiety" assessed at week 8 of the observational period.
- Mean change in scores of the Clinical Global Impression scale (CGI), item 2 (global improvement) at W2,W4,W8 assessed at week 8 of the observational period.
- Mean change from BL in total score of the SF-36 QoL questionnaire reported by patients at week 8 of the observational period.
- Mean change from BL in score of the SF-36 QoL questionnaire (physical component) reported by patients at week 8 of the observational period.
- Mean change from BL in score of the SF-36 QoL questionnaire (psychiatric component) reported by patients at week 8 of the observational period.

• Number of adverse events/ adverse drug reactions leading to drug discontinuation during the observational period.

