#### Data Management

- Data collection in this study is carried out using documentation forms. Centralized data entry will be performed by the responsible professional subcontractor for statistical analyses after receiving the documentation forms. The statistical analysis of the data and the creation of the final statistical report on the study will also be carried out by a responsible professional subcontractor for statistical analyses.
- Discrepancies will be resolved by mutual agreement between both parties (Servier and professional subcontractor for statistical analysis).

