#### **Biometrics**

- Due to the non-interventional nature of this study, statistical analysis will be conducted in a descriptive and searchable form. All indicators will be analyzed using descriptive statistics methods. For each indicator, the number of patients, the average value, the standard error, the minimum and maximum values, or the proportion of each category will be specified. All composite indicators will be
- listed and presented in visual form as graphs and frequency distribution tables / indicator tables.
- Absolute and percentage frequencies will be calculated for categorical variables. Only patients for whom data on the corresponding variables will be available will be included in the relative frequency calculations.
- All reports of adverse drug reactions, adverse events, and special situations will be coded using MedDRA, and the results will be listed and classified according to classes for organ and organ systems (system-Organ-Class; SOC) by the statisticial agency during preparation of final report.

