# Appendix 1. THE HAMILTON RATING SCALE FOR DEPRESSION (HAMD-17)

#### Instructions.

1

For assessment please choose one answer that best characterizes the patient's condition.

For item 7 (work and activities) the researcher can obtain information from relatives or medical personnel.

Item 16 (weight loss) requires an answer only by one of the proposed points 16A and 16B according to the "yes or no". The assessment of body weight changes is more preferable during therapy (16B). The assessment of weight change on anamnestic information (16A) is used only as initial, before starting therapy.

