#### Table for recording scores by Hamilton Depression Rating Scale

Total score by HAMD-17 scale:\_\_\_\_\_

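### Does the item 16 option numbered 3 for not assessed, or the remission cut-off below 7, leave the HAMD-17 results open to error?

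*Combined protocol and SAP*

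**What the plan says.** The primary variable is "Mean change from baseline (BL) in total HAMD-17 score assessed at week 8 of the observational period". The same total defines response ("HAMD-17 total score decrease ≥ 50" per cent) and "disease remission (defined as HAMD-17 total score < 7"), and inclusion criterion 4 sets entry at 8–24.

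Appendix 1 prints the scale. Items 16A (by history) and 16B (observed weekly loss) each have ratings 0, 1 and 2, followed by "3- Not assessed". The instruction reads "Item 16 (weight loss) requires an answer only by one of the proposed points 16A and 16B" and adds when each version applies; it does not say how the not-assessed option is scored. The recording table ends in a line for "Total score by HAMD-17 scale". The severity legend calls 0–7 normal.

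On data handling, Data Management says "Centralized data entry will be performed by the responsible professional subcontractor for statistical analyses after receiving the documentation forms", and Biometrics says "Only patients for whom data on the corresponding variables will be available will be included in the relative frequency calculations".

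**The concern.** There are two separate points.

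**Item 16.** The not-assessed option continues the same number series as the ratings, and the form asks for a sum. The instruction covers only the choice between 16A and 16B. The available-data sentence in Biometrics concerns percentages, not one missing item within a total. Data entry is central, but the text does not say whether totals are copied from the form or rebuilt from the items. An affected total could therefore be summed with the 3, summed without item 16, or treated as missing. The total feeds the primary variable, response, remission and entry, so a careless sum would reach all four.

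**Remission.** A patient who ends at exactly 7 falls in the protocol's normal band and below its entry floor, yet does not count as remitted. No reason is given, so the two passages can look inconsistent.

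**Working it through.** **Plan's own figure.** A one-sample t-test with one-sided alpha 0.005, SD 3.8 and a difference of 3.0 gives power 0.90991 at N = 28, as printed (N = 27 gives 0.896). Then 28 / (1 − 0.30) = 40, also as printed. Neither point changes any of these inputs.

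**Size per patient.** Nine items have a maximum of 4 and eight, including item 16, a maximum of 2: 9 × 4 + 8 × 2 = 52. Summing a 3 on item 16 would allow 53, above the scale's own maximum. If the true rating is r, the excess from adding the code is 3 − r, that is 3, 2 or 1 for r = 0, 1 or 2. With r = 0, a true baseline total of 5–7 would be recorded as 8–10 and look eligible. A true week-8 total of 4–6 would become 7–9 and lose remission.

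**Size in the mean.** Define improvement as V0 minus week 8.
- Coded at V0 only: improvement is overstated by the excess.
- Coded at week 8 only: improvement is understated by the excess.
- Coded at both: the error is (3 − r0) − (3 − r8) = r8 − r0, which is zero if the true ratings are equal.

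For patients coded at one visit only, with equal excess:

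bias in mean improvement = excess × (share coded at V0 only − share coded at week 8 only).

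The documents give no shares, so these are assumed:
- 5% at each visit: 3 × (0.05 − 0.05) = 0.
- 10% at one visit, none at the other: 0.1 to 0.3 points in size. The cited fall is 15.3 − 4.7 = 10.6, so this is 0.1/10.6 = 0.9% to 0.3/10.6 = 2.8%.
- 20% at one visit, none at the other, excess 3: 0.6 points, or 0.6/10.6 = 5.7%.
- A 1-point bias needs a net imbalance of 1/3 = 33% at the largest excess, and 100% at the smallest.

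**Would the code be noticed?** A 3 is out of range for item 16 wherever item scores are entered. Items 10 and 11 are secondary variables, so item-level data must be captured for at least part of the scale. The CGI form in Appendix 3 also puts its not-assessed code outside the rating range (0, with ratings 1–7). The number differs, but the role is the same.

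**Remission.** The only affected score is exactly 7. As an illustration, take the cited week-6 result (mean 4.7, SD 3.2, another population):
- Normal with continuity correction: P(≤ 6) = Φ((6.5 − 4.7)/3.2) = Φ(0.5625) = 0.713; P(≤ 7) = Φ(0.875) = 0.809; difference 0.096.
- The same normal truncated at −0.5: 0.697 and 0.799; difference 0.101 before rounding.
- Negative binomial with the same mean and SD: 0.754 and 0.826; difference 0.072.

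Remission would be about 70–75% below 7 and 80–83% at 7 or below. With 100 patients and the full 30% dropout, 70 are evaluable, and 70 × 0.072 to 70 × 0.101 is 5 to 7 patients. This is the difference between two valid definitions. It does not measure an error.

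**The case for a change.** The best case for a change is that a written rule costs one line, and that use of the code may be uneven. The instruction keeps 16A for before therapy and prefers 16B afterwards. 16B asks about weekly loss in kilograms, but Table 1 lists no weighing and the visits are at weeks 2, 4 and 8. The option could well be used more at week 8 than at V0, so the errors need not cancel. The two forms also use different numbers for not assessed (3 and 0), so no single numeric convention can be carried over.

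What stands is that the convention is unwritten in the legible text, and that imbalance is plausible. It does not follow that anyone would sum the code. If some did, heavier use at week 8 would understate improvement, so it would not flatter the drug. Eligibility is judged by the investigator at V0, before forms reach central data entry, so a central scoring rule would not protect the entry score.

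The obvious replacement is not clearly better. Prorating the other 16 items by 52/50 and rounding leaves a sum of 12 unchanged (12.48 to 12) but raises 13 to 14 (13.52). Near the cited means of 15.3 and 4.7, it would add a point at baseline and none at follow-up, enlarging the fall for a patient missing the item at both visits. It would also turn 24 into 25 (24.96), outside the entry range.

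On remission, the case is that readers may wonder why 7 is excluded. They can still see exactly which cut-off the rate uses. That a final 7 from a baseline of 8–13 is also a non-response follows from the 50% rule (7 is half of 14) and holds under either cut-off.

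**Conclusion.** No change follows. The item 16 point is a missing scoring detail that a competent analyst fills in one sensible way: an option labelled as a non-rating and lying outside 0–2 is missing and is not added. Even if it were added throughout, the mean change would move by at most 0.3 points per 10 percentage points of net imbalance between V0 and week 8, and by nothing if use and true ratings were balanced. Single patients near the entry or remission thresholds could be misclassified, but only if a site added the code.

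The remission point is a preference. Below 7 is a complete definition, the legend describes severity without defining remission, and a stricter endpoint is legitimate.

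This rests on two things. The frequency of the not-assessed option is unknown, so the shares above are illustrations. The recording table is only partly legible in the public text and may itself carry a scoring rule. The sample size of 28 evaluable and 40 enrolled is unaffected.

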#### INSIGHT

- 0- Acknowledges being depressed and ill
- 1- Acknowledges illness but attributes cause to bad food, climate, overwork, virus, need for rest, etc.
- 2- Denies being ill at all

#### Table for recording scores by Hamilton Depression Rating Scale

Total score by HAMD-17 scale:\_\_\_\_\_

# Assessment of the severity of condition using Hamilton Depression Rating Scale:

- 0-7 «normal» (no marked symptoms of anxiety and depression)
- 8-15 «mild depression»
- 16-24 «moderate depression»
- 25 and more «severe depression»

Appendix 2.

.

# Medical Outcomes Study Questionnaire Short Form 36 Health Survey (SF-36)

About: The SF-36 is an indicator of overall health status.

Items: 10

**Reliability:** Most of these studies that examined the reliability of the SF\_36 have exceeded 0.80 (McHorney et al., 1994; Ware et al., 1993). Estimates of reliability in the physical and mental sections are typically above 0.90.

Validity: The SF-36 is also well validated.

#### Scoring:

The SF-36 has eight scaled scores; the scores are weighted sums of the questions in each section. Scores range from 0 - 100 Lower scores = more disability, higher scores = less disability Sections:

- Vitality
- Physical functioning
- Bodily pain
- · General health perceptions
- · Physical role functioning
- Emotional role functioning
- Social role functioning
- Mental health

## Medical Outcomes Study Questionnaire Short Form 36 Health Survey

This survey asks for your views about your health. This information will help keep track of how you feel and how well you are able to do your usual activities. Thank you for completing this survey! For each of the following questions, please circle the number that best describes your answer.

1. In general, would you say your health	
is:	
Excellent	1
Very good	2
Good	3
Fair	4
Poor	5
2. Compared to one year ago,	
Much better now than one year ago	1
Somewhat better now than one year ago	2
About the same	3
Somewhat worse now than one year ago	4
Much worse now than one year ago	5

3. The following items are about activities you might do during a typical day. Does your health now limit you in these activities? If so, how much?

# (Circle One Number on Each Line)

	Yes, Limited a Lot (1)	Yes, Limited a Little (2)	No, Not limited at All (3)
a. Vigorous activities , such as running, lifting heavy objects, participating in strenuous sports	1	2	3
b. Moderate activities , such as moving a table, pushing a vacuum cleaner, bowling, or playing golf	1	2	3
c. Lifting or carrying groceries	1	2	3
d. Climbing several flights of stairs	1	2	3
e. Climbing one flight of stairs	1	2	3
f. Bending, kneeling, or stooping	1	2	3

g. Walking more than a mile	1	2	3
h. Walking several blocks	1	2	3
i. Walking one block	1	2	3
j. Bathing or dressing yourself	1	2	3

4. During the **past 4 weeks**, have you had any of the following problems with your work or other regular daily activities **as a result of your physical health**? (Circle One Number on Each Line)

	Yes	No
	(1)	(2)
a. Cut down the amount of time you spent on work or other activities	1	2
b. Accomplished less than you would like	1	2
c. Were limited in the kind of work or other activities	1	2
d. Had difficulty performing the work or other activities (for	1	2
example, it took extra effort)		

5. During the **past 4 weeks**, have you had any of the following problems with your work or other regular daily activities **as a result of any emotional problems** (such as feeling depressed or anxious)?

#### (Circle One Number on Each Line)

	Yes	No
a. Cut down the amount of time you spent on work or other	1	2
activities		
b. Accomplished less than you would like	1	2
c. Didn't do work or other activities as carefully as usual	1	2

6. During the past 4 weeks, to what extent has your physical health or emotional problems interfered with your normal social activities with family, friends, neighbors, or groups?	
Not at all	1
Slightly	2
Moderately	3
Quite a bit	4
Extremely	5

7. How much bodily pain have you had during the past 4 weeks?	
None	1
Very mild	2
Mild	3
Moderate	4
Severe	5
Very severe	6
8. During the past 4 weeks, how much did pain interfere with	
your normal work (including both work outside the home and	
housework)?	
Not at all	1
A little bit	2
Moderately	3
Quite a bit	4
Extremely	5

These questions are about how you feel and how things have been with you **during the past 4 weeks**. For each question, please give the one answer that comes closest to the way you have been feeling. (Circle One Number on Each Line)

	All of the Time	Most of the Time	A Good Bit of the Time	Some of the Time	A Little of the Time	None of the Time
a. Did you feel full of pep?	1	2	3	4	5	6
b. Have you been a very nervous person?	1	2	3	4	5	6
c. Have you felt so down in the dumps that nothing could cheer you up?	1	2	3	4	5	6
d. Have you felt calm and peaceful?	1	2	3	4	5	6
e. Did you have a lot of energy?	1	2	3	4	5	6

9. How much of the time during the past 4 weeks . . .

	All of the Time	Most of the Time	A Good Bit of the Time	Some of the Time	A Little of the Time	None of the Time
f. Have you felt	1	2	3	4	5	6
downhearted and blue?						
g. Did you feel worn out?	1	2	3	4	5	6
h. Have you been a happy	1	2	3	4	5	6
person?						
i. Did you feel tired?	1	2	3	4	5	6

10. During the past 4 weeks, how much of the time has your physical health or emotional problems interfered with your social activities (like visiting with friends, relatives, etc.)? (Circle One Number)	
All of the time	1
Most of the time	2
Some of the time	3
A little of the time	4
None of the time	5

# 11. How TRUE or FALSE is each of the following statements for you. (Circle One Number on Each Line)

	Definitely True	Mostly True	Don't Know	Mostly False	Definitely False
a. I seem to get sick a little easier than other people	1	2	3	4	5
b. I am as healthy as anybody I know	1	2	3	4	5
c. I expect my health to get worse	1	2	3	4	5
d. My health is excellent	1	2	3	4	5

# Appendix 3.

At ASSE and W0 visits, the global improvement (CGI-I) is not assessed.								
Cross the appropriate box.								
1. Severity of illness		2. Global improvement						
Considering your total experience with this particular population, how ill is the patient at this time?		Rate total improvement whether or not, in your judgement, it is due entirely to drug treatment. Compared to his condition at the inclusion visit how much has he changed?						
0	Not assessed	0 🗆	Not assessed					
□ 1	Normal, not at all ill	□ 1	Very much improved					
□ 2	Borderline mentally ill	□ 2	2 Much improved					
□ 3	Mildly ill	□ 3	Minimally improved					
□ 4	Moderately ill	□ 4	No change					
□ 5	Markedly ill	□ 5	Minimally worse					
□ 6	Severely ill	□ 6	Much worse					
□ 7	Among the most extremely ill patients	□ 7	Very much worse					

IC4-20098-069- RUSPlease send this form immediately by [contact] or by email to [contact], or pass to the associate of the company.								
Year of birth or Age Gend	er l	Height	Weight	Patient's ID	):			
or   N	ſ/F  _				_ _ _			
Description of adverse even	nt/reaction/spe	ecial situat	ion:	Date of ev	vent onset	Date of event   termination (in case   of recovery)		
Criteria of seriousness: DO YES (please, spec Death Hospitalization or Persistent or signi Congenital anoma Medically significa	Outcome:       Recovered       Recovered with consequences (persistent structural or functional impairment)       Not recovered       No recovered       Death       Unknown							
General disease(s) / Concomitant disease(s) (please indicate year when first diagnosed).								
Course adverse event/reaction/special situation (please enclose relevant findings, e.g. laboratory, hospital reports, histology, etc.):								
Causal relationship with intake of studied drug:       NO     YES     NOT APPLICABLE       If «Yes», please indicate dates of the use of studied drug in the first line of the table below:     If end to the use of studied drug in the first line of the table below:       If «No» or «Not applicable», please specify whether the adverse event/special situation is related to the medication of Servier company (which is specified in the table below):       NO     YES Please indicate the name of the medication of Servier company:								
List of current medications	Daily dose / route of administration	from	Dates of inta t	ke: o	Indication			
			-					
			-					
			-					
